6.4.2 Secondary Endpoint 2: Technical Success (Effectiveness)

Endpoint: A subject will be considered a Technical Success if percutaneous vascular closure is obtained with the MANTA device without the use of unplanned endovascular or surgical as collected on eCRFs.

Subjects to include: All subjects in Analysis Cohort with a procedure attempt will be included in this analysis.

Statistical analysis: The number of subjects and percentage of patients will be calculated for the percentage of subjects with technical success.

6.4.3 Secondary Endpoint 3: Ambulation Success (Effectiveness)

Endpoint: A subject will be considered an Ambulation Success if he/she is able to ambulate for at least 20 feet/6 meters without re-bleeding as collected on eCRFs.

Subjects to include: All subjects in Analysis Cohort with a procedure attempt will be included in this analysis.

Statistical analysis: The number of subjects and percentage of patients will be calculated for the percentage of subjects that are able to ambulate.

6.4.4 Secondary Endpoint 4: Time to Ambulation (Effectiveness)

Endpoint: The elapsed time between MANTA deployment (withdrawal of MANTA sheath from artery) and when ambulation is achieved (subject standing and walking at least 20 feet/6 meters without re-bleeding) as collected on eCRFs.

Subjects to include: All subjects in Analysis Cohort with a procedure attempt will be included in this analysis.

Statistical analysis: The time to ambulation will be summarized using descriptive statistics including mean, standard deviation, median, interquartile range, minimum and maximum, and mean time will be calculated.

6.4.5 Secondary Endpoint 5: Treatment Success (Effectiveness)

Endpoint: A subject will be considered a Treatment Success if he/she has Time to Hemostasis ≤10 minutes and has no LBAR Major Complications within 30 days.

Subjects to include: All subjects in Analysis Cohort with a procedure attempt will be included in this analysis.

Statistical analysis: The number of subjects and percentage of patients will be calculated for the percentage of subjects with treatment success.

6.4.6 Secondary Endpoint 6: Procedure Time (Effectiveness)

Endpoint: Defined as elapsed time from initial skin break (first needle insertion) to time when the post-deployment angiogram is completed as collected on eCRFs.

Subjects to include: All subjects in Analysis Cohort with a procedure attempt will be included in this analysis.

Statistical analysis: The procedure time will be summarized using descriptive statistics including mean, standard deviation, median, interquartile range, minimum and maximum will be calculated.

6.5 Secondary Endpoint 7: LBAR Minor Complications (Safety)

Endpoint: Large Bore Access-site Related VARC-2 Minor Vascular (LBAR Minor) Complication within 30 days (adapted from VARC-2 Definitions):

- Access site or access-related vascular injury (dissection, stenosis, perforation, rupture, arterio-venous fistula, pseudoaneurysms, hematomas, percutaneous closure device failure) not leading to death, life-threatening or major bleeding, visceral ischemia, or neurological impairment OR
- Distal embolization treated with embolectomy and/or thrombectomy and not resulting in amputation or irreversible end-organ damage OR
- Any unplanned endovascular stenting or unplanned surgical intervention not meeting the criteria for a major vascular complication OR
- Vascular repair or the need for vascular repair (via surgery, ultrasound-guided compression, transcatheter embolization, or stent-graft) OR
- Percutaneous closure device failure - Failure of a closure device to achieve hemostasis at the arteriotomy site leading to alternative treatment (other than manual compression or adjunctive endovascular ballooning).

AEs will be reviewed by the CEC and they will adjudicate whether an AE meets one or more of these events and this adjudication for endpoint classification will be used in analysis.

Subjects to include: All subjects in Analysis Cohort with a procedure attempt will be included in this analysis.

Statistical analysis: The number of subjects and percentage of patients will be calculated for the percentage of subjects with one or more LBAR Minor complication within 30 days.

6.6 Additional Analyses

Descriptive statistics will be used to report on the additional analyses. Comparisons may be made between subjects with and without LBAR Major or Minor Complications.

- Long-term LBAR Major and Minor complications
- Quantify Procedural and Post-procedural Characteristics such as:
 - Readmission rates within 30 days
 - Delayed ambulation for subjects with LBAR Major or LBAR Minor Complications
 - Delayed discharge for subjects with LBAR Major or LBAR Minor Complications
 - Use of adjunctive devices required at large bore access site (Angioseal, ProGlide, Prostar XL, balloon, stent, covered stent, or surgical repair)
- Subsequent Secondary Intervention(s) (For example, any additional surgical or percutaneous interventions post the index large bore procedure that occurred on the MANTA (ipsilateral) leg, such as percutaneous coronary intervention (PCI), through the 12 month follow-up phone call.)

6.7 Adverse Events and Device Deficiencies

Adverse events (AEs) and device deficiencies will be collected throughout this trial. AEs will be classified using the MedDRA coding system and will be summarized by System Organ Class and Preferred Term.

Adverse events that are determined to be related to the device or procedure (“associated with the target artery and/or the ipsilateral leg (not the contralateral side”) will be sent to the CEC for adjudication. The exact process will be finalized in the CEC charter. The CEC will adjudicate procedure and device relatedness of these events and whether events met an LBAR Major or Minor Complication. These adjudications will overrule investigator classifications for summarizing data.

For relatedness, classifications of Causal/Definite, Probably, Possible and Unknown (if any) will be considered related.

AEs will be summarized by count and proportion of subjects experiencing one or more events by seriousness, severity, device and procedure relatedness, and time period (day 0 (procedure)-discharge, discharge-30 days, 0-30 days, 31-60, 61-180 days, and 181-study exit).

Any UADEs, ADEs or SADEs will be summarized as well.

Device deficiencies collected on a separate eCRF form will also be summarized and indicate if any deficiencies resulted in any adverse events.

7 Poolability of Data

Analyses of the primary safety endpoint will be performed to assess the comparability of study sites. Sites with fewer than 5 subjects each will be included in summaries by site but excluded from poolability analysis.

LBAR Major Complications will be analyzed by Fisher's Exact test to assess if the Major Complication rates differ among study sites. If the study site rates differ ($p<0.15$) then additional analyses will be performed to explore the cause of the difference, in particular if the differences are caused by differences in some baseline factor.

8 Data Conventions and Missing Data

Every effort will be undertaken to limit premature discontinuations and ascertain completeness of data collection throughout the course of the study. It is unlikely that there would be missing data for the LBAR Major complication endpoint as a 30 day follow-up visit is typically standard of care for TAVR patients; therefore all subjects with an attempted procedure are expected to be followed for at least 30 days. The 12 month follow up assessment will be conducted via phone; sites will ensure that subject contact details are on file correctly when concluding the 30 day visit.

No imputations will be made for missing endpoint data. All available data will be summarized for any summary provided the subject has a procedure attempt.

If an onset date for an AE is incomplete, every effort will be made by the clinical team to identify and collect a valid date from the site, but in case any are incomplete, then the following rules will be used:

- If the day of the month is missing, the first of the month will be used unless it precedes the procedure date. Then the procedure date will be used.
- If the month is missing the date of the procedure will be used.
- No year is expected to be missing as the follow-up is quite short, but the date of procedure will be used if missing the year.

9 Appendices:

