## Schedule of Assessments

Table 1: Schedule of Assessments

Assessment	Screening Visit	TAVR Procedure	Closure Procedure			Post-procedure	Discharge	Follow-up (FUP)	
			Pre-closure	Closure	Post-closure			30-day office visit (±7 Days)	12-month Phone (±30 Days)
Subject Eligibility / Informed Consent / Applicable PHI Authorization form*	X								
Medical History	X								
Medications 	X	X	X	X	X	X	X	X	X
Laboratory Tests	X 								
Pregnancy Test	X 								
CT Angiographic Scan	X 								
Ultrasound  (access and assessment)		X		X					
ACT / SBP			X 						
Adjunctive Devices				X	X				
Target Femoral angiography					X 				
Target Femoral access site assessment					X	X	X	X	X 
Time to Hemostasis					X 				
Delayed Ambulation/Discharge						X	X		
Adverse Events			X	X	X	X	X	X	X 
Subsequent Secondary Intervention 							X	X	X

\*Or other form required by applicable U.S. or Canadian laws governing the use and disclosure of individually identifiable protected health information (PHI)

1. The following medications will be recorded on the eCRF for each subject: cardiovascular medications (e.g., anti-hypertensives, anti-arrhythmic, etc.), anti-coagulants, anti-thrombotic and anti-platelets. Any changes to these medications should be documented throughout the course of the 12 month follow up.
2. Considered standard of care and are to be done according to the site's standard of care practice for pre-procedure labs for the TAVR procedure (hemoglobin, creatinine, and platelet count, International Normalized Ratio (INR))
3. Screening Visit CT Scan to assess both limbs for presence/absence/severity of calcium, atherosclerotic disease, tortuosity, and acceptable flow rates
4. Ultrasound for access SOC; Ultrasound data collection during closure
5. Prior to all closure methods, record ACT and systolic BP (per MANTA VCD warnings SBP<180mmHg; recommend ACT<250 seconds prior to closure but these targets are not mandatory per protocol; capturing ACT and SBP prior to closure is mandatory)
6. Post-closure, perform target (ipsilateral) femoral angiography from contralateral access site to ensure patency into the ipsilateral common femoral artery
7. At 12m follow-up, target femoral access site assessment will be questions completed via phone; adverse events will only pertain to target access site

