## 9. Study Follow up Visits

### 9.1. 30 Day Office Visit

The following evaluations will be performed in the office/clinic at 30 days ( $\pm$  7 days) post procedure:

- Assess any changes to medications
- Adverse events
- Target Femoral access site assessment
- Any subsequent secondary interventions since discharge (For example, any new surgical or percutaneous interventions post the index large bore procedure that occurred on the femoral artery of the MANTA (ipsilateral) leg, such as percutaneous coronary intervention (PCI), through the 12 month follow-up phone call.)

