## 9.2. 12-month Phone Assessments

The following assessments will be collected via phone at 12 months ( $\pm$  30 days) post procedure:

- Assess any changes to medications
- Adverse event inquiry (specific to adverse events related to the MANTA leg and/or a MANTA related adverse event between 30 days and 12 months)
- Target Femoral access site assessment question
- Any subsequent secondary interventions since the 30-day visit (For example, any new surgical or percutaneous interventions post the index large bore procedure that occurred on the femoral artery of the MANTA (ipsilateral) leg, such as percutaneous coronary intervention (PCI), through the 12 month follow-up phone call.)

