### 11.6. AE and Serious Adverse Event (SAE) Reporting to Sponsor

All SAEs, irrespective of potential causal relationship to the device, procedure or study, that occur from the point of attempted MANTA VCD placement (including U/S use post TAVR completion and prior to MANTA VCD use) onwards will be reported to the Sponsor within 24

hours of the Investigator's first knowledge of the event. Suspected SAEs also should be reported.

The Investigator will forward information, via the eCRF system, about an SAE promptly, even if the information is incomplete or it is obvious that more data will be needed to form any conclusions. This information will be available to the Sponsor and CRO in the database. Additional information regarding the SAE will be recorded on the follow-up AE form forwarded to the Sponsor.

All AEs should be reported on the eCRF as soon as practicably possible. AEs will be recorded by their final medical diagnosis and not by each separate symptom. The information for the event will include the date of awareness, onset and resolution, the action taken, the corrective treatment and how the subject recovered with or without sequelae. In case of death, the relationship of death to the investigational device and/or the study procedure will be well documented. The date on which subject expired, what attempts were made to treat the event that led to death, the performance and functioning of the device during the event will be noted.

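### SAP 6.7 tabulates all AEs to study exit, but after the 30-day visit only MANTA-leg or MANTA-related AEs are asked about, so the later all-AE rows are under-ascertained and not comparable with days 0-30

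*SAP*

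**What the plan says.** SAP 6.7 opens with "Adverse events (AEs) and device deficiencies will be collected throughout this trial". It then plans the summary: "AEs will be summarized by count and proportion of subjects experiencing one or more events by seriousness, severity, device and procedure relatedness", and by "time period (day 0 (procedure)-discharge, discharge-30 days, 0-30 days, 31-60, 61-180 days, and 181-study exit". No scope limit or caveat is attached to the periods after day 30.

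The protocol collects AEs in two different ways:

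- **30-day visit (Protocol 9.1).** "The following evaluations will be performed in the office/clinic at 30 days", with a window of 7 days either side. Adverse events are listed without restriction.
- **12-month call (Protocol 9.2).** "The following assessments will be collected via phone at 12 months", with a window of 30 days either side. The AE item reads "Adverse event inquiry (specific to adverse events related to the MANTA leg and/or a MANTA related adverse event between 30 days and 12 months". Note 7 of the Protocol's Schedule of Assessments is narrower: "adverse events will only pertain to target access site". The SAP carries the same note under its own Table 1 (Section 2.1).

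Separately, Protocol 11.6 makes "All SAEs, irrespective of potential causal relationship to the device, procedure or study" reportable from the attempted placement onward, within 24 hours of the investigator first learning of them.

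**The concern.** One table would combine two ascertainment rules. Up to the 30-day visit the site asks about any AE. After it, the one planned contact asks only about the treated leg or the device. A fall in the proportion of subjects with an AE, an SAE or a not-related AE after day 30 could therefore come from the narrower question rather than from the patients, and nothing in the SAP would tell the reader so. At stake is the 12-month safety description in the final report.

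**Working it through.** No stated sample size, rate or error level enters this point. The check sets the reporting periods against the contacts that feed them.

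**Contact windows**

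- 30-day visit: 30 ± 7 = days 23 to 37.
- 12-month call, taking 12 months as day 365: 365 ± 30 = days 335 to 395.
- Gap between the two contacts: from 335 − 37 = 298 days to 395 − 23 = 372 days.

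**Periods against contacts**

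| SAP 6.7 period | Scheduled contact inside it | AE scope at that contact |
|---|---|---|
| Day 0 to discharge; discharge to 30; 0-30 | Procedure, post-procedure, discharge, 30-day visit | Any AE |
| 31-60 | None, unless the 30-day visit falls on days 31-37 | Any AE, if so |
| 61-180 | None | (asked about only later, at the 12-month call) |
| 181 to exit | 12-month call | MANTA leg and/or MANTA-related (9.2); target access site (note 7) |

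**Which later rows fall outside the call's question**

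- Target-leg and MANTA-related AEs: inside the scope of 9.2. The weakness here is recall over about 11 months, not scope.
- Procedure-related AEs: Protocol 11.4 counts events from the TAVR itself and from closure of a non-target access site. These are outside the question unless they involve the MANTA leg.
- Not-related AEs: outside, unless in the MANTA leg.
- All AEs and serious AEs: a mixture. The out-of-scope part depends on reports that nobody is scheduled to ask for.

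**Illustration of the size (assumed values; none is in the documents)**

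Let f be the share of true AEs after day 30 that are MANTA-leg or MANTA-related, all captured at the call. Let c be the share of the other AEs captured by unsolicited report. Then

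captured fraction = f + (1 − f) × c

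| f | c | Captured fraction |
|---|---|---|
| 0.05 | 0 | 0.05 |
| 0.10 | 0 | 0.10 |
| 0.10 | 0.25 | 0.10 + 0.90 × 0.25 = 0.325 |
| 0.10 | 0.50 | 0.10 + 0.90 × 0.50 = 0.55 |
| 0.50 | 0.50 | 0.50 + 0.50 × 0.50 = 0.75 |

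The fraction reaches 1 only if c = 1 or f = 1. The width of this range shows that the documents do not fix the shortfall.

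**Two related details in SAP Section 8**

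- An AE with no onset month is dated to the procedure. A late event recalled vaguely at 12 months would move into the day 0 to discharge period.
- All available data are summarised for anyone with a procedure attempt. As written, nothing keeps a subject lost before the call from counting as event-free in the later periods.

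**The case against.** The case on the other side has real substance.

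- **Other routes stay open.** Protocol 11.6 keeps SAEs of any cause reportable once known. Protocol 11.3 accepts AEs volunteered at any time, and Protocol 16.5 has source documents reviewed for unreported AEs. The 12-month call also asks about medication changes and ipsilateral interventions, which may bring other events to light. This stands: later events are under-ascertained, not absent. But these routes depend on the site happening to learn of an event, and the one planned contact is not designed to find it.
- **11.6 and 9.2 need not conflict.** One is a duty that starts with knowledge; the other says what a call asks. This stands. The firmer wording conflict is between 9.2 and note 7. Protocol 11.3 also has the investigator determine at each later evaluation whether any AE occurred, which sites could read as wider than either.
- **A period without a contact is not in itself a defect.** AEs can be placed by onset date, and the call looks back to day 30. This stands, so the three periods need not be merged.
- **The table is supportive.** SAP 6.2 makes the remaining endpoints descriptive and rests approval on the primary analysis report. SAP Section 1 defers layouts to a separate template, which could carry a footnote. This limits the importance of the point, but the SAP text itself sets no limit.

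A reader might go further and try to count the missing subjects. An assumed SAE rate of 15-30% between day 31 and month 12 gives 150 × 0.15 = 22.5 to 150 × 0.30 = 45 subjects, against 150 × 1/81 = 1.9 from the MARVEL long-term subset (Protocol 3.4). The documents do not support that contrast. The SAE rate is not in them, the MARVEL figure counts VARC-2 Major or Minor complications (a narrower class than the call asks about), and unsolicited SAE reports are left out.

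**Conclusion.** The point holds as a mismatch between table and data collection. After the 30-day visit, which may be as late as day 37, AEs outside the MANTA leg and unrelated to MANTA are no longer solicited, yet SAP 6.7 reports them to study exit as if they were. This covers about 11 of the 12 months of follow-up. The all-AE, serious, not-related and non-target procedure-related rows after day 30 should not be compared with the 0-30 day rows.

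It would be tempting to infer that every later row other than the target-leg and MANTA-related ones is wrong. The documents show only that those rows are incomplete to an unknown degree.

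The primary endpoint and the LBAR VARC-2 Minor endpoint are within 30 days and are untouched. The long-term LBAR analysis falls inside the scope of the call. The conclusion assumes that sites follow the specific text for the call in 9.2 or note 7. It needs no assumed event rate.

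**What to change.** 1. **SAP 6.7, to day 30:** limit the all-AE tables to the periods up to day 30.
2. **SAP 6.7, after day 30:** tabulate only target-leg or MANTA-related AEs, and say so in the title. Report beside the table how many subjects completed the 12-month contact, died or were lost. Keep every subject with a reported event in the count, including those lost later.
3. **SAEs:** keep the all-cause duty in Protocol 11.6 and have the existing 12-month call also ask about deaths and all SAEs, so that an all-SAE row after day 30 has a solicited basis. If that question is not added, label the row as unsolicited reports only.
4. **Wording:** reconcile Protocol 9.2 (MANTA leg and/or MANTA-related) with note 7 in both schedules (target access site only), and state how Protocol 11.3 applies to the call.

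Cost: a SAP table edit, one added question in a call already planned, and a protocol wording change, which under Protocol Section 19 needs IRB/REB and regulatory review. No visit, sample size or primary analysis changes.

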### **7.7. Withdrawal**

Subjects must be informed about their right to withdraw from the study at any time and for any reason without sanction, penalty, or loss of benefits to which the subject is otherwise entitled. Withdrawal from the study will not jeopardize their future medical care or relationship with the investigator. Subjects will be asked to specify the reason for their termination, but have the right not to answer.

The investigator may decide to withdraw a subject from the study at any time with reasonable rationale. The subject's future care will not be influenced by a decision, voluntary or otherwise, to withdraw from the study. All reasonable efforts should be made to retain the subject in the study until completion of the study.

If a subject withdraws from the study, the site will record the subject's reasons for withdrawal on the End of Study CRF.

Possible reasons for withdrawal include:

- Adverse Event
- Subject is unwilling or unable to comply with follow up requirements
- Explantation of device
- Subject withdraws consent and/or PHI authorization
- Subject is Lost to Follow up after 3 attempts to reach out to the subject with final attempt documented on a registered letter.
- Investigator determines that the subject should no longer continue in the study
- Death

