#### **15.3.5. *Timing of Reports***

IDE annual progress reports will be submitted as required per applicable law and regulations. A primary analysis report will be submitted to FDA to support a PMA supplement for revised labeling when the first 75 PAC subjects have completed their 30 day follow-up visit. A final clinical study report will be submitted once all 150 PAC subjects have been enrolled, completed all follow-up visits and have exited the study.

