#### **15.5. *Missing Data***

Every effort will be undertaken to limit premature discontinuations and ascertain completeness of data collection throughout the course of the study. It is unlikely that there would be missing data for the LBAR VARC-2 Major complication endpoint as a 30 day follow-up visit is typically standard of care for TAVR patients; therefore all subjects with an attempted procedure are expected to be followed for at least 30 days. The 12 month follow up assessment will be conducted via phone; sites will ensure that subject contact details are on file correctly when concluding the 30 day visit.

Missing data will not be imputed, and all available data will be summarized.

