Based on these results, the population LBAR Major complication rate is hypothesized to be 4.2%, the weighted average of the above rates. Examining the confidence intervals above, the upper confidence limits for comparably-sized studies range from 5.4% to 19.9%, corresponding to point estimates of 1.0% to 10.7%. A performance goal of 14.2%, which is based on clinical judgement regarding device performance, falls well within this range, indicating that it is constructed in a fashion consistent with prior findings in the literature.

Additionally, though Sponsor does not intend to demonstrate better safety outcomes than with use of the current approved procedure, determining deployment depth of MANTA using the depth locator, the value of 14.2% is more stringent than the performance goal of 19.9% which was accepted for the MANTA VCD PMA study.

Using these inputs, a one-sided alpha of 0.025 and at least 80% power, 69 subjects will provide adequate power to reject the primary safety hypothesis. To ensure an adequate sample size of subjects meeting the 30-day primary safety endpoint, and to account for patient attrition, data from the first 75 consecutive subjects (with a maximum of 15 subjects at any one site to cap enrollment at 20% of subjects enrolled per site) in the Primary Analysis Cohort (PAC) will be analyzed and submitted as to support a PMA supplement for revised labeling to include the U/S-guided method.

Additional subjects will be enrolled as part of the PAC to provide supplementary data in support of future publications for a total of 150 enrolled subjects (with a maximum of 30 subjects at any one site to cap enrollment at 20% of subjects enrolled per site) in the overall study.

Additionally, roll-in subjects (up to 2 per operator per site) using the MANTA VCD will be enrolled to allow investigators to learn how to use the U/S guided therapy with the MANTA VCD. This group will be analyzed separately and not count towards the PAC.

The rate of LBAR Major Complications within 30 days of the procedure will be presented along with the exact one-sided upper 97.5% confidence bound. If this upper confidence bound is less than 14.2%, the study will have met its primary objective.

6 Statistical Analyses and Study Objectives

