6.2 Timing of Reports

In addition to the required IDE annual progress reports, there will be two reports prepared: the primary analysis report once 75 subjects have completed their 30 day follow-up (see details below), and a Final Report.

The primary analysis report will be prepared once the first 75 consecutively enrolled subjects in the PAC have either completed their 30 day visit or withdrawn from the trial. The primary safety endpoint will include subjects from the 75 subjects only unless more than 15 subjects have been enrolled at a single site. If this unlikely situation occurs, then the first 15 enrolled subjects from that site will be included to achieve no more than 20% of patients coming from a single site. All remaining endpoints will summarize what data are available at that time as endpoints are intended to be descriptive in nature and involve no hypothesis testing.

A final report will be prepared once the trial is complete, where all subjects have completed their 12 month visit or withdrawn from the study and sites are closed. All available subject data will be included at this time. A 95% confidence interval for the main safety endpoint will still be prepared but the basis for approval is intended to use the primary analysis report.

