6.3 Primary Safety Endpoint: LBAR Major complications

Endpoint: Large Bore Access-site Related VARC-2 Major Vascular (LBAR Major) Complication within 30 days (adapted from VARC-2 Definitions)¹⁰

- Access site or access-related vascular injury (dissection, stenosis, perforation, rupture, arterio-venous fistula, pseudoaneurysm, hematoma, irreversible nerve injury, compartment syndrome, percutaneous closure device failure) leading to death, life threatening or major bleeding, visceral ischemia, or neurological impairment OR
- Distal embolization (noncerebral) from a vascular source requiring surgery or resulting in amputation or irreversible end-organ damage OR

- The use of unplanned endovascular or surgical intervention associated with death, major bleeding, visceral ischemia or neurological impairment OR
- Any new ipsilateral lower extremity ischemia documented by patient symptoms, physical exam, and/or decreased or absent blood flow on lower extremity angiogram OR
- Surgery for access site-related nerve injury OR
- Permanent access site-related nerve injury

AEs will be reviewed by the CEC to determine if they meet one or more of these criteria and this adjudication for endpoint classification will be used in analysis.

Hypothesis:

The primary safety hypothesis is that the LBAR Major complication rate (proportion of subjects with one or more) is less than the Performance Goal of 14.2%, as follows:

$$H_0: \pi \geq 0.142$$

vs.

$$H_A: \pi < 0.142,$$

where π is the population LBAR Major Complication rate within 30 days.

The primary safety hypothesis is that the rate of LBAR Major complications within 30 days of the procedure is less than the performance goal of 14.2%.

Stated in words, the hypothesis is:

Null hypothesis: The rate of LBAR Major complications within 30 days of the procedure not less than the performance goal of 14.2%

Alternate hypothesis: The rate of LBAR Major complications within 30 days of the procedure is less than the performance goal of 14.2%

Subjects to include:

The first 75 chronologically enrolled subjects in the Analysis Cohort where an attempt to use the MANTA device is made (enrolled subjects without an attempt will not be included).

Statistical Analysis:

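### Does the lack of a stated rule for subjects with unknown day-30 status, and of a sensitivity analysis for them, put the primary safety test at risk?

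*SAP*

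**What the plan says.** SAP section 6.3 defines the primary set as "The first 75 chronologically enrolled subjects in the Analysis Cohort where an attempt to use the MANTA device is made". It sets no condition on follow-up to day 30. The endpoint is the proportion of subjects with at least one major access-site complication, as adjudicated by the events committee. It is tested with an exact binomial test at one-sided 0.025 against 14.2%.

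SAP section 6.2 starts the primary report once these subjects "have either completed their 30 day visit or withdrawn from the trial", so early leavers can be among the 75. Protocol section 15.3.5 words the trigger more narrowly: "when the first 75 PAC subjects have completed their 30 day follow-up visit".

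On missing data, SAP section 8 says "No imputations will be made for missing endpoint data" and then adds "All available data will be summarized for any summary provided the subject has a procedure attempt". Protocol section 15.5 agrees: "Missing data will not be imputed, and all available data will be summarized". Both sections expect few missing outcomes, because a 30-day visit is usual care after TAVR.

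SAP section 5 finds that 69 subjects are enough and sets 75 with this reason: "To ensure an adequate sample size of subjects meeting the 30-day primary safety endpoint, and to account for patient attrition". Neither document plans a worst-case or tipping-point analysis of the primary endpoint.

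**The concern.** The texts seem to pull against each other. If all 75 stay in the denominator, a subject who left on day 10 without an event counts as event-free for 30 days. That looks like an imputation, which SAP section 8 rules out. If such subjects are dropped, as the step from 69 to 75 suggests, the set is no longer the 75 named in section 6.3.

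The test is single-arm, its endpoint is harm, and SAP section 6.2 makes this report the intended basis for approval. Events that nobody sees can only turn a pass into a fail. The margin is thin: 4 events in 75 pass and 5 fail, so one unseen event would reverse a 4-event pass. The planned report would not show how many unseen events it would take. A choice of denominator made after the count is known could also be questioned.

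**Working it through.** **Inputs.** Goal 14.2%, assumed rate 4.2%, one-sided alpha 0.025, 69 needed and 75 analysed (SAP sections 5 and 6.3). The allowance for attrition is 75 − 69 = 6 subjects (8% of 75). The documents give no dropout rate, so the number of unknowns *m* is an assumption, shown from 0 to 7.

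**Formulas.** With *x* events in *n* subjects, the exact upper 97.5% bound *U* solves P(X ≤ x | n, U) = 0.025. The study passes if U < 14.2%. With a limit of *c* events, the pass probability at true rate *p* is P(X ≤ c | n, p).

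**The plan's own figure.** At n = 69 the limit is 4 events (U for 4/69 = 14.18%). P(X ≤ 4 | 69, 0.142) = 0.0248 and P(X ≤ 4 | 69, 0.042) = 0.836. At n = 68 the limit falls to 3 and power to 68.0%. So 69 reproduces.

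**The two readings.** Dropping uses n = 75 − m. Keeping uses 75 with unknowns as non-events, where 4/75 gives 13.10% (pass) and 5/75 gives 14.88% (fail). The last two columns assume the same event rate in leavers and stayers.

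| Unknown m | Known n | Limit if dropped | U for 4/n | Limit if kept | P(pass) at 14.2% | P(pass) at 4.2% |
|---|---|---|---|---|---|---|
| 0 | 75 | 4 | 13.10% | 4 | 1.34% | 79.3% |
| 1 | 74 | 4 | 13.27% | 4 | 1.49% | 80.0% |
| 3 | 72 | 4 | 13.62% | 4 | 1.83% | 81.5% |
| 6 | 69 | 4 | 14.18% | 4 | 2.48% | 83.6% |
| 7 | 68 | 3 | 14.38% | 4 | 0.91% dropped, 2.74% kept | 68.0% dropped, 84.3% kept |

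From m = 0 to 6 the limit is 4 under both readings, so the verdict is the same and the false-pass probability stays under 2.5%. At m = 7 they part: with 4 events, keeping passes and dropping fails.

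**Unseen events.** Counted on 75, a pass with 0, 1, 2, 3 or 4 observed events is lost if 5, 4, 3, 2 or 1 unknowns are in truth events. The chance of that, given a pass, is

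Σ(x = 0 to 4) P(X = x | 75 − m, 0.042) × P(Y > 4 − x | m, r) ÷ P(X ≤ 4 | 75 − m, 0.042),

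where *r* is an assumed event rate after last contact:

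| m | r = 0.5% | r = 2% | r = 4.2% |
|---|---|---|---|
| 1 | 0.1% | 0.4% | 0.9% |
| 3 | 0.3% | 1.3% | 2.7% |
| 6 | 0.6% | 2.4% | 5.2% |

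The right-hand column gives leavers the full 30-day rate again from last contact, although the schedule has already checked them for events through closure, post-procedure and discharge.

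**The case for a change.** The best case for a change does not rest on the denominator. An expectation that data will be complete is not a rule, and the same plan sets aside six subjects for attrition. The verdict can be close: at 4.2% with 72 known subjects, P(X = 4) = 0.173 and P(X = 3) = 0.229 out of a pass probability of 0.815, so 21% of passes sit at 4 events and 28% at 3. As subjects are lost the limit stays at 4, so the test becomes slightly easier to pass. A table of tipping counts costs almost nothing, and fixing the rule beforehand removes any suspicion that it was chosen to suit the result.

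Part of this stands. The treatment of early leavers is not spelled out, and a table would be a fair courtesy to the reader. But the drift in pass probability within the allowance is the discreteness of an exact test moving from 75 back to the 69 for which it was sized, and it stays within alpha. The table would not be a success rule, and the tipping counts follow from the limit of 4 by subtraction.

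The obvious remedy, keeping all 75 and counting unknowns as no event, is the weaker choice in the only range where the choice matters. At seven unknowns it gives a false-pass probability of 2.74%, while available-case analysis lowers the limit to 3 events and gives 0.91%.

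Chart or phone checks would largely repeat what the protocol already asks. Section 15.5 commits to complete data collection, section 7.7 classes a subject as lost only after repeated contact ("Subject is Lost to Follow up after 3 attempts to reach out to the subject"), section 11.6 requires serious events within 24 hours, and section 16.5 has source records searched for unreported events. Section 7.7 also lists death and adverse events as reasons for withdrawal, and those often come with a known status.

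**Conclusion.** No change follows. This is a detail left unstated that an analyst can fill sensibly. SAP section 8's available-data sentence supports counting adjudicated events among attempted subjects whose status is known. For 0 to 6 unknowns the alternative reading gives the same decision, at most 4 events. Seven or more unknowns, over 9% of 75, would exceed the plan's own allowance.

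The differing triggers are a matter of wording: SAP section 6.2 first repeats the completed-visit condition, then adds withdrawals as detail.

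What remains is a chance of up to 2.7% with three unknowns, or 5.2% with six, that unseen events would have overturned a pass. A sensitivity display would describe that risk without reducing it.

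The conclusion rests on three assumptions: no more than six unknowns; leavers whose event rate after last contact is not above the plan's 4.2%; and, for the 2.48% figure, leaving unrelated to outcome. If many subjects were lost, or lost because of access-site trouble, the question would need to be reopened when the data are reported.
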